## 5.2 Exclusion Criteria

Subjects **may not** enter the study if they fulfill any of the following criteria:

1.	Treatment with an investigational agent within 4 weeks of starting treatment, and any prior drug-related toxicity (except alopecia) should have recovered to Grade 1 or less.
2.	Prior treatment with anti-CTLA-4 therapy.
3.	Active, suspected or prior documented autoimmune disease or inflammatory disorders (including but not restricted to inflammatory bowel disease [e.g., colitis or Crohn's disease], celiac disease, diverticulitis [with the exception of diverticulosis], Sarcoidosis syndrome, Wegner's granulomatosis with polyangiitis, Hashimoto's thyroiditis, rheumatoid arthritis, systemic lupus, Graves' disease, rheumatoid arthritis, hypophysitis, uveitis, scleroderma and its variants, multiple sclerosis, myasthenia gravis, etc. ). Vitiligo, alopecia, residual hypothyroidism (e.g., following Hashimoto syndrome) due to autoimmune condition only requiring hormone replacement, psoriasis or any chronic skin condition not requiring systemic treatment, or conditions not expected to recur in the absence of an external trigger are permitted. Subjects without active disease in the last 5 years may be included but only after consultation with the study physician. Subjects with celiac disease controlled by diet alone may also be included.
4.	Subjects with clinically significant cardiovascular disease, including: 
 
a. New York Heart Association (NYHA) Class II or higher congestive heart failure.
 
b. Myocardial infarction, unstable angina, cerebrovascular accident or transient ischemic attack within 6 months of Day 1.
 
c. Clinically significant supraventricular or ventricular arrhythmia.
 
d. QTcF ≥ 450 ms (male) or QTcF ≥ 470 ms (female).
 
e. Clinically uncontrolled hypertension.
 

5.	History of pneumonitis or interstitial lung disease, or any unresolved immune-related adverse events following prior therapy.
6.	Major surgery within 4 weeks of starting treatment (or scheduled for surgery during the projected course of the study).
7.	Women of child bearing potential who are pregnant as evidenced by positive serum pregnancy test (minimum sensitivity 25 IU/L or equivalent units of HCG) or nursing.
8.	Female subjects of childbearing potential who are sexually active with a non-sterilized male partner must use at least one highly effective method of contraception (see table below) from the time of screening and must agree to continue using such precautions for 90 days after the last dose of durvalumab or for 6 months after the last dose of tremelimumab (whichever is longer). Non-sterilized male partners of a female subject

CONFIDENTIAL

must use male condoms plus spermicide throughout this period. Cessation of birth control after this point should be discussed with a responsible physician. Not engaging in sexual activity for the total duration of the drug treatment and the drug washout period is an acceptable practice; however, periodic abstinence, the rhythm method, and the withdrawal method are not acceptable methods of contraception.

Female subjects should refrain from breastfeeding throughout the period described above.

Females of childbearing potential are defined as those who are not surgically sterile (i.e., bilateral tubal ligation, bilateral oophorectomy, or complete hysterectomy) or post-menopausal.

Females will be considered post-menopausal if they have been amenorrheic for 12 months without an alternative medical cause. The following age-specific requirements apply:

- Females <50 years of age would be considered post-menopausal if they have been amenorrheic for 12 months or more following cessation of exogenous hormonal treatments and if they have luteinizing hormone and follicle-stimulating hormone levels in the post-menopausal range for the institution or underwent surgical sterilization (bilateral oophorectomy or hysterectomy).
- Females ≥50 years of age would be considered post-menopausal if they have been amenorrheic for 12 months or more following cessation of all exogenous hormonal treatments, had radiation-induced menopause with last menses >1 year ago, had chemotherapy-induced menopause with last menses >1 year ago, or underwent surgical sterilization (bilateral oophorectomy, bilateral salpingectomy or hysterectomy).

**Non-sterilized male subjects** who are sexually active with a female partner of childbearing potential must use male condoms plus spermicide from screening through 90 days after last dose of durvalumab or through 6 months after the last dose of tremelimumab (whichever is longer). Female partners of childbearing potential of a male subject must use a highly effective method of contraception (see table below) throughout this period. Cessation of birth control after this point should be discussed with a responsible physician. Not engaging in sexual activity for the total duration of the trial and the drug washout period is an acceptable practice; however, periodic abstinence, the rhythm method, and the withdrawal method are not acceptable methods of contraception.

Male subjects should refrain from sperm donation throughout the period described above.

Highly effective methods of contraception are described in the table below. A highly effective method of contraception is defined as one that results in a low failure rate (i.e. less than 1% per year) when used consistently and correctly. Note that some contraception methods are not considered highly effective (e.g. male or female condom with or without spermicide; female cap, diaphragm, or sponge with or without spermicide; non-copper containing intrauterine device; progestogen-only oral hormonal

CONFIDENTIAL

	
contraceptive pills where inhibition of ovulation is not the primary mode of action [excluding Cerazette/desogestrel which is considered highly effective]; and triphasic combined oral contraceptive pills).
 
Acceptable highly effective methods of contraception are described in the following table:
 
  
 Highly Effectivea Methods of Contraception	
 
 Barrier/Intrauterine Methods	Hormonal Methods	
   
  
 
Copper T intrauterine device
 
Levonorgestrel-releasing intrauterine system (e.g., Mirena®)b
 
 	 
 
“Implants”: Etonogestrel-releasing implants: e.g., Implanon® or Norplan®
 
“Intravaginal Devices”: Ethinylestradiol/etonogestrel-releasing intravaginal devices: e.g., NuvaRing®
 
“Injection”: Medroxyprogesterone injection: e.g., Depo-Provera®
 
“Combined Pill”: Normal and low dose combined oral contraceptive pill
 
“Patch”: Norelgestromin/ethinylestradiol-releasing transdermal system: e.g., Ortho Evra®
 
“Minipillc”: Progesterone based oral contraceptive pill using desogestrel: e.g., Cerazette®
 
 	
 
  
a - Highly effective (i.e. failure rate of <1% per year)
 
b - This is also considered a hormonal method
 
c - Cerazette® is currently the only highly effective progesterone based pill.
 	
  
	Highly Effective a Methods of Contraception		Barrier/Intrauterine Methods	Hormonal Methods	
 
Copper T intrauterine device
 
Levonorgestrel-releasing intrauterine system (e.g., Mirena®)b
 
	
 
“Implants”: Etonogestrel-releasing implants: e.g., Implanon® or Norplan®
 
“Intravaginal Devices”: Ethinylestradiol/etonogestrel-releasing intravaginal devices: e.g., NuvaRing®
 
“Injection”: Medroxyprogesterone injection: e.g., Depo-Provera®
 
“Combined Pill”: Normal and low dose combined oral contraceptive pill
 
“Patch”: Norelgestromin/ethinylestradiol-releasing transdermal system: e.g., Ortho Evra®
 
“Minipillc”: Progesterone based oral contraceptive pill using desogestrel: e.g., Cerazette®
 
	
a - Highly effective (i.e. failure rate of <1% per year)
 
b - This is also considered a hormonal method
 
c - Cerazette® is currently the only highly effective progesterone based pill.
	
Highly Effective a Methods of Contraception									
Barrier/Intrauterine Methods	Hormonal Methods								

 
Copper T intrauterine device
 
Levonorgestrel-releasing intrauterine system (e.g., Mirena®)b
 
	
 
“Implants”: Etonogestrel-releasing implants: e.g., Implanon® or Norplan®
 
“Intravaginal Devices”: Ethinylestradiol/etonogestrel-releasing intravaginal devices: e.g., NuvaRing®
 
“Injection”: Medroxyprogesterone injection: e.g., Depo-Provera®
 
“Combined Pill”: Normal and low dose combined oral contraceptive pill
 
“Patch”: Norelgestromin/ethinylestradiol-releasing transdermal system: e.g., Ortho Evra®
 
“Minipillc”: Progesterone based oral contraceptive pill using desogestrel: e.g., Cerazette®
 
								

a - Highly effective (i.e. failure rate of <1% per year)
 
b - This is also considered a hormonal method
 
c - Cerazette® is currently the only highly effective progesterone based pill.
									
9.	Subjects who are immunosuppressed, including those with known immunodeficiency.								
10.	Active infection including tuberculosis (clinical evaluation that includes clinical history, physical examination and radiographic findings, and TB testing in line with local practice), hepatitis B (known positive HBV surface antigen (HBsAg) result and/ or HBV DNA), hepatitis C (defined as presence of HCV RNA), or human immunodeficiency virus (positive HIV 1/2 antibodies) and/or known HIV carrier. Subjects with a past or resolved HBV infection (defined as the presence of hepatitis B core antibody [anti-HBc] and absence of HBsAg) are eligible. Subjects positive for hepatitis C (HCV) antibody are eligible only if polymerase chain reaction is negative for HCV RNA.								
11.	History of severe allergic reactions to any unknown allergens or components of the study drugs (see specific exclusions for BI 1361849 below).								
12.	Uncontrolled intercurrent illness, including but not limited to, ongoing or active infection, bleeding disorders, symptomatic congestive heart failure, uncontrolled hypertension, unstable angina pectoris, cardiac arrhythmia, interstitial lung disease, or serious chronic gastrointestinal conditions associated with diarrhea.								
13.	Mental impairment or social situations that may compromise compliance with the requirements of the study or compromise the ability of the subject to give written informed consent.								
14.	Lack of availability for immunological and clinical follow-up assessment.								
15.	
 
Allergy to any components of BI 1361849 protamine sulfate (e.g. allergy to protamine-containing insulins), or fish allergy, or prior vasectomy (as it may
 
								

CONFIDENTIAL

	
increase the risk of protamine allergy), or known Type I allergy to beta-lactam antibiotics.
 
 
• Skin disease (e.g., psoriasis) that may prevent intradermal administration of the vaccine into the target areas.
 
• Prior cancer vaccine treatment or allogeneic bone marrow transplantation.
 
• Any previous vaccination or immunotherapy (including any treatments that have immunostimulatory properties such as mistletoe extract) within 2 weeks prior to Day 1
 
• History of splenectomy.
 
• Requirement for chronic immunosuppressive treatment including daily systemic steroid doses of <math>\geq 10</math> mg prednisone equivalent per day.
 
• Any severe systemic infection which continued until 2 weeks prior to Day 1.
 

16.	Any condition that, in the clinical judgment of the treating physician, is likely to interfere with the interpretability of the data or prevent the subject from complying with any aspect of the protocol or that may put the subject at unacceptable risk.
17.	Subjects must not donate blood while on study and for at least 90 days following the last durvalumab treatment or for 6 months after the last dose of tremelimumab (whichever is longer).
18.	History of allogeneic organ transplant.
19.	History of leptomeningeal carcinomatosis.
20.	Active or prior malignancy except for history of other prior malignancy treated with curative intent which, in the opinion of the treating investigator and the Sponsor, has minimal risk of interfering with safety or efficacy endpoints of the study.

CONFIDENTIAL

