  - Total bilirubin  $\leq 5$  times ULN that downgrades to Grade  $\leq 2$  ( $\leq 3$  times ULN) within 7 days after onset, whereby maximal supportive care, including systemic corticosteroids, is permitted.
  - Grade  $\geq 3$  neutropenia that (1) is not associated with fever or systemic infection, (2) does not require medical intervention, and (3) improves to Grade 2 within 7 days.
  - Grade 3 and 4 lymphopenia.
  - Grade 3 thrombocytopenia that (1) is not associated with clinically significant bleeding, (2) does not require medical intervention, and (3) improves to Grade 2 within 7 days.
  - Isolated Grade 3 electrolyte abnormalities that are not associated with clinical signs or symptoms and are reversed with appropriate maximal medical intervention within 3 days.
  - Any pre-existing laboratory abnormality that deteriorates to Grade 3/4, but where the increment of deterioration is considered not clinically significant by both investigator and sponsor.
  - Grade 3 or 4 asymptomatic increases in amylase or lipase levels for which appropriate evaluation shows no clinical evidence of pancreatitis.

Immune-related AEs (irAEs) are defined as AEs of immune nature (i.e., inflammatory) in the absence of a clear alternative etiology. In the absence of clinical abnormality, repeat laboratory testing will be conducted to confirm significant laboratory findings prior to designation as a DLT.

While rules for adjudicating DLTs are specified above, an AE that is Grade < 3 or listed as exempt above may also be defined as DLT after consultation with the sponsor and Investigators, based on the emerging safety profiles of durvalumab, tremelimumab, and BI 1361849. Likewise, subjects who become not evaluable for DLT, because they discontinued or interrupted treatment due to toxicities other than DLTs, may be counted as DLT subjects, if the toxicities cannot be managed in accordance with the dosing modifications described in Section 3.1.8.

Subjects who experience a DLT will be discontinued from study treatment and will enter the On Study and Post Study Follow-up (see Section 3.1.16). However, if it is in the best interest of the subject, the Investigator, subject and Sponsor may agree to continue treatment with BI 1361849.

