### 7.1.2.1 Pregnancy

#### 7.1.2.1.1 Maternal Exposure

Female subjects should avoid becoming pregnant and breastfeeding during the study and for 90 days after the last dose of durvalumab or for 6 months after the last dose of tremelimumab, whichever is longer (see Section 5.2, #8).

If a subject becomes pregnant during the course of the study, the study drugs should be discontinued immediately.

Pregnancy itself is not regarded as an AE unless there is a suspicion that the drug under study may have interfered with the effectiveness of a contraceptive medication. Congenital abnormalities or birth defects and spontaneous miscarriages should be reported and handled as SAEs (see Section 7.1.6). Elective abortions without complications should not be handled as AEs. The outcome of all pregnancies (spontaneous miscarriage, elective termination, ectopic pregnancy, normal birth, or congenital abnormality) should be followed up and documented even if the subject was discontinued from the study.

If any pregnancy occurs in the course of the study, the Investigator or other site personnel should inform the Sponsor within 1 day, i.e., immediately, but **no later than 24 hours** of when he or she becomes aware of it.

The Sponsor will work with the Investigator to ensure that all relevant information is provided within 1 to 5 calendar days for SAEs and within 30 days for all other pregnancies.

The same timelines apply when outcome information is available.

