#### 7.1.2.1.2 Paternal Exposure

Male subjects should refrain from fathering a child or donating sperm during the study and for 90 days after the last dose of durvalumab or for 6 months after the last dose of tremelimumab, whichever is longer (see Section 5.2, #8).

Pregnancy of the subject's partner is not considered to be an AE. However, the outcome of all pregnancies (spontaneous miscarriage, elective termination, ectopic pregnancy, normal birth, or congenital abnormality) occurring from the date of the first dose until 90 days after the last dose should, if possible, be followed up and documented.

---

CONFIDENTIAL

Where a report of pregnancy is received, prior to obtaining information about the pregnancy, the Investigator must obtain the consent of the subject's partner. Therefore, the local study team should adopt the generic ICF template in line with local procedures and submit it to the relevant Ethics Committees (ECs)/Institutional Review Boards (IRBs) prior to use.

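### Exclusion #8 ties the end of required contraception only to the antibodies, so it can lapse while a subject kept on BI 1361849 alone is still being vaccinated

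*Protocol*

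**What the plan says.** Exclusion #8 in Protocol Section 5.2 starts contraception at screening. Women of childbearing potential are held to the following: "continue using such precautions for 90 days after the last dose of durvalumab or for 6 months after the last dose of tremelimumab", with the later date applying. For non-sterilized men the text reads "must use male condoms plus spermicide from screening through 90 days after last dose of durvalumab or through 6 months after the last dose", the drug in that last dose being tremelimumab and the later date again applying. Two further limits borrow the same period: "Female subjects should refrain from breastfeeding throughout the period described above" and "Male subjects should refrain from sperm donation throughout the period described above". The vaccine appears in none of these sentences.

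The abstinence alternative in the same criterion is framed differently. For women it reads "Not engaging in sexual activity for the total duration of the drug treatment and the drug washout period is an acceptable practice"; for men it spans the trial plus washout.

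Section 3.1.9 makes stopping all study treatment the default after a DLT, but adds that, if it serves the subject's interest, "the Investigator, subject and Sponsor may agree to continue treatment with BI 1361849".

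Two later sections point back to #8 and word the period differently. Section 7.1.2.1.1: "Female subjects should avoid becoming pregnant and breastfeeding during the study and for 90 days after the last dose of durvalumab", or 6 months after tremelimumab if longer. Section 7.1.2.1.2: "Male subjects should refrain from fathering a child or donating sperm during the study and for 90 days after the last dose of durvalumab", with the same tremelimumab alternative. Section 7.1.2.1.2 also follows partner pregnancies until 90 days after the last dose, without saying of which drug.

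**The concern.** The protocol foresees subjects who receive BI 1361849 without the antibodies. For them, #8 counts its end date from a drug they no longer take, so the period can run out while vaccination continues. Sections 7.1.2.1.1 and 7.1.2.1.2 cite #8 as though the periods were the same, yet they add the time on study.

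#8 does not permit conception on the vaccine, because the 7.1.2.1 sections still forbid it. The trouble is that #8 is the only place that says which contraceptive method is required, and its end date is the shorter one. A site applying it literally would stop requiring a highly effective method while the subject still receives an investigational product and is still scheduled for pregnancy tests. What is at stake is reproductive safety in a small group, not any estimate or analysis.

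**Working it through.** **Inputs**
- Cycles of 28 days, 12 cycles (Section 3.1.7).
- Vaccination days from the Section 3.2 flowchart: 1, 8, 15, 29, 43, 57, 71, 85, 113, 141, 183, 225, 267, 309 (14 in all).
- Durvalumab on Day 1 of every cycle; tremelimumab on Day 1 of Cycles 1 to 4, so last on Day 85 (flowchart).
- DLT evaluation period: the first 2 cycles (Section 3.1.9). A DLT in that window therefore puts the last antibody dose on Day 1 or Day 29. A later DLT also ends treatment (Section 3.1.10).
- Assumption: 6 months is 181 to 184 days, depending on the calendar.

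**Check of the flowchart's own figure.** Day 1 of cycle c = 1 + 28 × (c − 1). For c = 12 this is 1 + 28 × 11 = 309, as printed.

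**Arm A.** End of the #8 period = last durvalumab day + 90. Gap = 309 − end.

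| Last durvalumab | #8 ends | Days before Day 309 | Vaccinations still scheduled |
|---|---|---|---|
| Day 1 | Day 91 | 218 | 6 |
| Day 29 | Day 119 | 190 | 5 (Days 141, 183, 225, 267, 309) |
| Day 57 | Day 147 | 162 | 4 |
| Day 85 | Day 175 | 134 | 4 |
| Day 113 | Day 203 | 106 | 3 |
| Day 141 | Day 231 | 78 | 2 |
| Day 169 | Day 259 | 50 | 2 |
| Day 197 | Day 287 | 22 | 1 |
| Day 225 | Day 315 | no gap | 0 |

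**Arm B, both antibodies last given the same day.** The 6-month limit is always later than the 90-day one, so end = that day + 181 to 184.

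| Last dose of both | #8 ends | Days before Day 309 | Vaccinations still scheduled |
|---|---|---|---|
| Day 1 | Day 182–185 | 124–127 | 3 or 4 |
| Day 29 | Day 210–213 | 96–99 | 3 |
| Day 57 | Day 238–241 | 68–71 | 2 |
| Day 85 | Day 266–269 | 40–43 | 1 or 2 |

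If tremelimumab is completed on Day 85 and durvalumab stops on Day 113, 141 or 169, the 90-day limit (Day 203, 231 or 259) is earlier than Day 266, so the last row still applies. A last durvalumab dose on Day 197 gives Day 287 with 1 vaccination left; Day 225 gives Day 315 and no gap.

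**Pregnancy tests after release.** For the Arm A Day 29 case, the flowchart still schedules tests on Days 169, 225 and 281 and at 28 and 91 days after the last dose: 309 + 28 = 337 and 309 + 91 = 400. Five tests fall after Day 119.

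**Full schedule.** With durvalumab to Day 309, #8 ends on Day 309 + 90 = 399, after the last vaccination. The gap belongs only to subjects who lose durvalumab by Cycle 8 and stay on the vaccine.

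**The case against.** The strongest reply is that the rest of the protocol already covers this. Sections 7.1.2.1.1 and 7.1.2.1.2 forbid pregnancy, breastfeeding, fathering a child and sperm donation while on study. #8 itself asks that stopping birth control be discussed with a physician. Pregnancy, or the intent to become pregnant, ends study treatment (Section 3.1.10), and pregnancy test results must be reviewed before dosing (flowchart footnote a). The abstinence wording suggests that coverage throughout treatment was intended, which makes this a drafting slip. Vaccine-only treatment needs three-party agreement, and Section 8.4 stops the vaccine for several serious toxicities. Nor does any document show a reproductive hazard: Section 1.2.3 reports preclinical local breakdown with an average half-life of 2 days and no detectable systemic RNA.

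Much of this stands. It limits the size of the problem, and for breastfeeding and sperm donation the mismatch is one of dates only, because the 7.1.2.1 sections restrict both directly. The lack of a shown hazard is a good reason not to add a waiting period after the last vaccine dose.

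It does not close the gap in method. The 7.1.2.1 sections state an outcome to avoid and name no contraceptive. The physician discussion applies only once the stated period is over. Tests and withdrawal rules detect or respond to a pregnancy; they do not prevent one. A slip in a safety instruction still misdirects a site that follows it.

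**Conclusion.** The point holds. For subjects continued on BI 1361849 after the antibodies stop, #8 gives an end date that can precede the last vaccination and disagrees with the two sections that cite it. Within the DLT evaluation period the lapse can reach 190 days and 5 vaccinations (last durvalumab Day 29) or 218 days and 6 vaccinations (Day 1) in Arm A. In Arm B it can reach about 96 to 127 days and 3 or 4 vaccinations. There is no gap once durvalumab reaches Day 225.

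These figures assume nominal visit days and that every later vaccination is given through Day 309, so they are upper limits. The documents do not say how many subjects received the vaccine alone; the conditions on that route suggest few. The conclusion does not depend on the vaccine carrying a known reproductive risk. It rests on the protocol's own rule that pregnancy is to be avoided throughout the study. No endpoint, population or analysis is touched.

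**What to change.** In both the female and male paragraphs of exclusion #8, insert *throughout study treatment, including BI 1361849, and* before the 90-day/6-month period. The breastfeeding and sperm-donation sentences then follow without editing, because they refer to the same period. A subject vaccinated through Cycle 12 would be covered to at least Day 309, with no vaccination falling after release. No separate interval after the last vaccine dose is proposed.

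The consent form was not available for this review; conform it only if it carries the same end dates.

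The cost is one phrase in each of two paragraphs, any matching consent change, and a longer contraception requirement for the few subjects on the vaccine alone.
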